7.3. Reporting Requirements for this Study

The PI or clinical site personnel should notify Covance PSS of all SAEs, regardless of relationship to the investigational drug, within 24 hours of clinical site personnel becoming aware of the event. The PI (or designee) will provide the initial notification by sending a completed SAE form which must include the PI's (or designee's) assessment of the relationship of the event to investigational drug and must be signed by the PI. Follow-up information, or new information regarding an ongoing SAE, must be provided promptly to Covance DSS at the study agents for which expedited reporting are required are:

• EIDD-2801 or Placebo for EIDD-2801

The investigator will attempt to establish a diagnosis of the event based on signs, symptoms, and/or other clinical information. Whenever possible, the diagnosis (not the individual signs/symptoms) will be documented as the AE/SAE.

Additionally, all reported pregnancies from the day of randomization through 50 days (for female participants) or 100 days (for female partners of male participants) after the last dose of study intervention must be reported to the sponsor by the investigator.

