- DESIGN This is a Phase IIa, double-blind, placebo-controlled, randomized trial designed to compare the safety, tolerability, and antiviral activity of EIDD-2801 (also known as MK-4482) versus placebo as measured by viral RNA detection in symptomatic adult outpatients with coronavirus disease-2019 (COVID-19).
- DURATION 28 days. Treatment will be for 5 days with 23 days of post-treatment followup.
- SAMPLE SIZE This study will enroll up to approximately 172 fully evaluable participants in multiple study parts. If participants in a dose group drop out or otherwise have missing or unevaluable primary or key secondary virology endpoint data, additional participants may be enrolled to ensure adequate data at each dose level. The total number of participants to be enrolled will not exceed 204.

Part 1:

- Arm A (EIDD-2801 200 mg): up to approximately 22 participants
- Arm B (placebo): up to approximately 22 participants

Parts 2-4 (Optional):

- Arms C (Part 2), E (Part 3), G (Part 4) (EIDD-2801 up to 800 mg): up to approximately 12 participants per part
- Arms D (Part 2), F (Part 3), H (Part 4) (placebo): up to approximately 4 participants per part

Parts 5-9 (Optional):

- Arms I, K, M, O, Q (EIDD-2801 up to 800 mg): up to approximately 12 participants per part
- Arms J, L, N, P, R (placebo): up to approximately 4 participants per part

The dose of EIDD-2801 evaluated in Part 1 will be 200 mg BID. Doses selected for subsequent study parts may be the same, higher or lower than doses studied in previous Part(s), and will not exceed 800 mg BID. Doses

will be chosen based on emerging virology and safety data from this study and other ongoing clinical studies. Selected doses will be communicated in an official memo/protocol clarification letter. The maximum number of participants enrolled will be 204. Participants who are randomized but do not start study treatment will be replaced. All study part sizes are approximate. Study parts may be combined for randomization purposes if the same dose is planned for more than one part. Study parts enrolling at the same dose level may be enrolled simultaneously.

Study Part	Treatment Arm	Placebo Arm	Total Subjects	Projected Dose
	(n)	(n)		Level
1	A (22)	B (22)	44	200 mg
2	C (12)	D (4)	16	400 mg
3	E (12)	F (4)	16	400 mg
4	G (12)	H (4)	16	400 mg

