5. STUDY TREATMENT

5.1. Regimens, Administration, and Duration

Doses of EIDD-2801 and matching placebo will be formed from combinations of

. In Part 1 of the study, participants will be randomized 1:1 to receive one of the following two regimens:

- ARM A:
 - Day 1-5: EIDD-2801 200 mg orally BID for 5 days.
- ARM B:
 - Days 1-5: Placebo for EIDD-2801 orally BID for 5 days.

An optional Part 2 may be initiated in which patients will be randomized 3:1 (active:placebo) to receive one of the following two regimens:

- ARM C: Day 1-5: EIDD-2801 up to 800 mg orally BID for 5 days.
- ARM D:

Days 1-5: Placebo for EIDD-2801 orally BID for 5 days.

An optional Part 3 may be initiated in which patients will be randomized 3:1 (active:placebo) to receive one of the following two regimens:

- ARM E:
 - Day 1-5: EIDD-2801 up to 800 mg orally BID for 5 days.
- ARM F:

Days 1-5: Placebo for EIDD-2801 orally BID for 5 days.

An optional Part 4 may be initiated in which patients will be randomized 3:1 (active:placebo) to receive one of the following two regimens:

- ARM G:
 - Day 1-5: EIDD-2801 up to 800 mg orally BID for 5 days.
- ARM H: Days 1-5: Placebo for EIDD-2801 orally BID for 5 days.

Additional optional Parts 5-9 may be initiated in which patients will be randomized 3:1 (active:placebo) to receive one of the following two regimens:

- ARM I (Part 5), K (Part 6), M (Part 7), O (Part 8), Q (Part 9):
 - Day 1-5: EIDD-2801 up to 800 mg orally BID for 5 days.
- ARM J (Part 5), L (Part 6), N (Part 7), P (Part 8), R (Part 9): Days 1-5: Placebo for EIDD-2801 orally BID for 5 days.

Each participant will begin study treatment dosing with the first dose on Day 1 and the second dose at least 4 hours later on Day 1. If the first dose on Day 1 is a late evening dose, the second dose may be taken on the morning of Day 2, in which case the final dose will be taken on the morning of Day 6. In addition, if a participant misses up to 2 doses during Days 1 to 5, dosing may be extended into Day 6.

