6.1.5. End of Study Evaluations

Participants will undergo an in-clinic evaluation on Day 28 for an End of Study visit.

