6.2.15. Pregnancy Testing

Pregnancy testing:

- Pregnancy testing requirements for study inclusion are described in Section 4.1.
- High sensitivity pregnancy testing should be conducted at screening (serum or urine) within 24 hours of the first dose of study drug and on Day 28 (serum) approximately 23 days after the last dose of study intervention.
- Additional serum or urine pregnancy tests may be performed, as determined necessary by the investigator or required by local regulation, to establish the absence of pregnancy at any time during the subject's participation in the study.

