7.3.5. Pregnancy and Exposure During Breastfeeding

If a pregnancy is reported, the investigator will record pregnancy information on the appropriate form and submit it to the sponsor within 24 hours of learning of the pregnancy in a female participant or female partner of male participant (after obtaining the necessary signed informed consent from the female partner).

Although pregnancy and infant exposure during breastfeeding are not considered AEs, any pregnancy or infant exposure during breastfeeding in a participant (spontaneously reported to the investigator or their designee), including the pregnancy of a male participant's female partner, that occurs during the study are reportable to the Sponsor as described in Section 7.3.

All reported pregnancies must be followed to the completion/termination of the pregnancy.

Any pregnancy complication will be reported as an AE or SAE.

The medical reason (example: maternal health or fetal disease) for an elective termination of a pregnancy will be reported as an AE or SAE. Prenatal testing showing a fetus will be born with severe abnormalities/congenital anomalies that leads to an elective termination of a pregnancy will be reported as an SAE for the fetus.

Pregnancy outcomes of ectopic pregnancy, spontaneous abortion, missed abortion, benign hydatidiform mole, blighted ovum, fetal death, intrauterine death, miscarriage, and stillbirth must be reported as serious events (Important Medical Events). If the pregnancy continues to term, the outcome (health of infant) must also be reported.

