8.2. Adverse Events

Adverse events will be coded using MedDRA[®] (Medical Dictionary for Regulatory Activities) Version 23. Any events reported after the initiation of study treatment and up to 14 days after the last dose of study treatment are defined as treatment-emergent AEs (TEAEs). AEs started more than 14 days after the last dose of study treatment will be considered post treatment and will be summarized separately

Adverse event summarizes will summarize only TEAEs. Adverse events will be categorized by TEAE, serious TEAE (SAE), death, and discontinuation. These categories will be further summarized by the causal relationship to study drug (Related and Possible related will be grouped together as Related; AEs Reported as Unlikely and Not Related will be grouped together as Not Related).

The Investigator will provide an assessment of the intensity of each AE. Intensity will be assessed in terms of severity (mild, moderate, severe, potentially life-threatening or death). Subjects will be counted once and summarized under their highest severity within a SOC and PT.

The following TEAE summary tables will be prepared:

• Overall Summary of TEAEs (Any TEAE, TEAE Related to study drug, Grade 2 or higher TEAE, Grade 3 or higher TEAE, Drug related TEAEs, Drug related Grade 3 or higher

TEAE, TEAEs leading to study drug discontinuation, Drug related TEAEs leading to study drug discontinuation, Serious TEAE, TEAE leading to death)

- Summary of TEAEs by SOC and PT
- Summary of TEAEs by maximum severity SOC, and PT
- Summary of Grade 2 or higher TEAEs by SOC and PT
- Summary of Grade 3 or higher TEAEs by SOC and PT
- Summary of Drug Related Grade 3 or higher TEAEs by SOC and PT
- Summary of Drug Related TEAEs by SOC, and PT
- Summary of TEAEs resulting in discontinuation from study drug by SOC and PT
- Summary of Drug Related TEAEs resulting in discontinuation from study drug by SOC and PT
- Summary of Serious TEAEs by SOC and PT
- Summary of Drug Related Serious TEAEs by SOC and PT
- Summary of Post Treatment AEs by SOC and PT

8.3. **Pregnancies (as applicable)**

If any female subjects become pregnant during the study, a listing will be provided.

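### SAP 8.3 lists only female participants' pregnancies during the study, so partner pregnancies and those after Day 28, which Protocol 7.3 makes reportable, fall outside the planned listing

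*Protocol*

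**What the plan says.** **Reporting window.** Protocol 7.3 makes reportable "all reported pregnancies from the day of randomization through 50 days (for female participants) or 100 days (for female partners of male participants", in each case after the last dose. The contraception commitments in the inclusion criteria (4.1.10 and 4.1.11) run for the same 50 and 100 days.

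**Follow-up.** The protocol synopsis states: "Treatment will be for 5 days with 23 days of post-treatment followup". Section 6.1.5 closes the schedule: "Participants will undergo an in-clinic evaluation on Day 28 for an End of Study visit". The last planned pregnancy test, for women of childbearing potential, is "on Day 28 (serum) approximately 23 days after the last dose of study intervention" (6.2.15). The Schedule of Events shows no later visit, call or test. The vital-status follow-up in 6.2.12 applies only to participants who leave the study early.

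**How pregnancies become known.** Protocol 7.3.5 describes a pregnancy in a participant as "spontaneously reported to the investigator or their designee" and includes partners of male participants. It then says that a pregnancy "that occurs during the study are reportable to the Sponsor as described in Section 7.3". Once the investigator learns of a pregnancy, it goes to the sponsor within 24 hours and is followed to its end.

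**Planned output.** SAP 8.3 has one sentence: "If any female subjects become pregnant during the study, a listing will be provided". The SAP's section on changes from the protocol (Section 11) names two changes, the unstratified log-rank test and the dropping of formal safety comparisons. It does not mention pregnancy.

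**The concern.** The protocol defines a population (female participants and partners of male participants) and a time window. The SAP output is narrower on both counts, and nothing in the SAP says the narrowing is deliberate. A programmer following SAP 8.3 would leave out a partner pregnancy reported on Day 20, and a participant's pregnancy reported on Day 40, although Protocol 7.3 covers both.

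The second strand is ascertainment. The reporting window outlasts the schedule of contacts, so its later part depends on someone volunteering the information.

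At stake is how the pregnancy data will be read. Protocol 2.5.1 records that the drug and its metabolite were mutagenic in a bacterial assay. Protocol 2.10 says that no safety data exist in pregnant women and explains why women of childbearing potential are nonetheless enrolled. Enrolment is capped at 204, so any pregnancies will probably be few and each matters. An empty listing could be taken to cover the 50- and 100-day windows when it covers neither in full.

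**Working it through.** **Inputs.** Last dose on Day 5, or Day 6 under the late-start variant in Protocol 5.1, "in which case the final dose will be taken on the morning of Day 6". Last scheduled contact on Day 28 (6.1.5). Windows of 50 and 100 days after the last dose (7.3), starting at randomization, taken as Day 1.

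**The plan's own figure.** Days from last dose to the Day 28 test = 28 − last-dose day. This gives 28 − 5 = 23, and 28 − 6 = 22 for the variant. The approximate 23 days in Protocol 6.2.15 is reproduced.

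**Days after the last scheduled contact.**
- Window end = last-dose day + 50 (female participants) or + 100 (partners).
- Days after last contact = window end − 28.
- Share of post-dose days = days after last contact ÷ 50 or ÷ 100.
- Share of whole window = days after last contact ÷ window end (counting from Day 1).

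| Last dose | Group | Window ends | Days after Day 28 | Share of post-dose days | Share of whole window |
|---|---|---|---|---|---|
| Day 5 | Female participants | 5 + 50 = Day 55 | 55 − 28 = 27 | 27/50 = 54% | 27/55 = 49% |
| Day 5 | Partners | 5 + 100 = Day 105 | 105 − 28 = 77 | 77/100 = 77% | 77/105 = 73% |
| Day 6 | Female participants | 6 + 50 = Day 56 | 56 − 28 = 28 | 28/50 = 56% | 28/56 = 50% |
| Day 6 | Partners | 6 + 100 = Day 106 | 106 − 28 = 78 | 78/100 = 78% | 78/106 = 74% |

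Protocol 7.3 starts the window at randomization, so the last column follows its wording most closely. For partners the table is, if anything, generous: the protocol describes no scheduled partner test or question even before Day 28.

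**Scope of the listing, side by side.** This part does not depend on how days are counted.

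| Pregnancy | Reportable under Protocol 7.3? | In the SAP 8.3 listing? |
|---|---|---|
| Female participant, by Day 28 | Yes | Yes |
| Female participant, after Day 28, within 50 days of last dose | Yes | No |
| Partner, by Day 28 | Yes | No |
| Partner, after Day 28, within 100 days of last dose | Yes | No |

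The second row reads the SAP's study period as ending on Day 28, as Protocol 4.1.7 does when it gives the study period as 28 days. The partner rows follow from the listing being confined to female subjects.

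**Timing of lock.** SAP 4.2 runs the final analysis on the locked database once the last subject completes the study. For a man who is the last to complete, his partner's window would still have 77 or 78 days to run at his Day 28 visit.

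**The case against.** The strongest reply is that the protocol has a working route for these pregnancies and never promised surveillance. Section 7.3 concerns pregnancies that are reported. Section 7.3.5 gives the mechanism: volunteered report, submission within 24 hours, partners included with consent, follow-up to outcome, and complications and adverse outcomes handled as adverse or serious events. Participants carry a card with site contact details (6.2.8). The consent pages were removed from the documents reviewed and may tell participants to report later pregnancies. Eligibility requires contraception or abstinence over the same windows. Pregnancy is neither an objective nor an endpoint, and the expected count may be close to zero.

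Much of this stands, and it rules out three stronger readings that a reader might infer:

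- **That later pregnancies go unascertained.** They are not actively solicited; a volunteered report is still captured and followed to its end.
- **That most of the window is uncovered for everyone.** This is true for partners. For female participants it is about half, and 49–50% when counted from randomization as 7.3 does.
- **That partner and late pregnancies could not appear in any report.** They reach the sponsor through the safety route, and SAP Section 1 permits supplementary analyses identified in the study report. The gap is in the planned listing.

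The reply does not answer the mismatch itself. Having a route to the sponsor does not put a pregnancy into SAP 8.3, and permission to add analyses is not a plan to do so. A consent-form instruction would still be passive, and would not alter the SAP or the wording of 7.3.5.

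**Conclusion.** The point holds as a mismatch of scope between documents, together with passive ascertainment after Day 28. SAP 8.3 omits partner pregnancies altogether and participants' pregnancies after Day 28, although Protocol 7.3 makes both reportable. Protocol 7.3.5 and 7.3 state different periods and need to be reconciled. The part of the window resting on volunteered reports is 49–56% for female participants and 73–78% for partners.

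These figures assume last dosing on Day 5 or 6, a Day 28 visit on its nominal day (its window is not legible in the extracted schedule), and no later contact arranged in documents not available here. They are shares of calendar time, not estimates of missed pregnancies; the documents give no basis for such a count.

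The consequence is limited to the completeness and labelling of pregnancy safety data. No efficacy estimate, power or type I error figure changes. It is worth correcting because the SAP change costs almost nothing and brings the output into line with the protocol's own window.

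**What to change.** 1. **SAP 8.3.** List all pregnancies in participants and in partners of male participants reported within the Protocol 7.3 windows, showing treatment group, whether participant or partner, and days since last dose. Give those reported after database lock in a dated supplement, so that the main analysis need not wait. The cost is a sentence or two of SAP text and a small later data cut.
2. **Protocol 7.3.5.** Reconcile its reporting period with 7.3. In the same edit, Protocol 2.5.6 needs reconciling with the rest of the protocol, since it assigns both the 50-day and the 100-day period to female participants. The cost is wording only.
3. **Preferably, one brief remote query** about pregnancy at the end of each window: women of childbearing potential at 50 days after the last dose, men at 100 days. Sites already hold participants' contact details and secondary contacts (Protocol 3.2 and 6.2.7). The cost is one extra contact per relevant participant, a consent-form line if none exists, and the late data cut. Items 1 and 2 do not depend on it.
4. **Until this is done,** label any empty listing as covering only female participants' known pregnancies through Day 28.

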7.3.1. Laboratory Test Abnormalities

Laboratory abnormalities present at the screening visit will be recorded as pre-treatment signs and symptoms. After study treatment administration, a clinical laboratory abnormality should be reported as an AE only if it is considered clinically significant by the investigator.

In addition, the following laboratory abnormalities should also be captured on the AE CRF page as appropriate:

- Any laboratory test result that is clinically significant or meets the definition of an SAE
- Any laboratory abnormality that required the participant to have the investigational product discontinued or interrupted
- Any laboratory abnormality that required the participant to receive specific corrective therapy

It is expected that wherever possible, the clinical diagnosis would be used by the reporting investigator (e.g., anemia versus low hemoglobin value).

7.3.2. Grading Severity of Events

The DAIDS AE Grading Table, corrected Version 2.1, July 2017, must be used and is available on the DAIDS RSC website at https://rsc.niaid.nih.gov/clinical-research-sites/daids-adverse-event-grading-tables.

When changes in severity of an AE occur, the maximum severity for the experience should be noted.

7.3.3. Relationship

The relationship of an AE to the administration of the study drug is to be assessed by the investigator according to the following definitions:

- No (unrelated, not related, no relation): The time course between the administration of study drug and the occurrence or worsening of the AE rules out a causal relationship and another cause (concomitant drugs, therapies, complications, etc.) is suspected.
- Yes (related): The time course between the administration of study drug and the occurrence or worsening of the AE is consistent with a causal relationship and no other cause (concomitant drugs, therapies, complications, etc.) can be identified.

The following factors should also be considered:

- The temporal sequence from study drug administration The event should occur after the study drug is given. The length of time from study drug exposure to event should be evaluated in the clinical context of the event.
- Underlying, concomitant, intercurrent diseases Each report should be evaluated in the context of the natural history and course of the disease being treated and any other disease the participant may have.
- Concomitant medication The other medications the participant is taking or the treatment the participant receives should be examined to determine whether any of them might be recognized to cause the event in question.
- Known response pattern for this class of study drug Clinical and/or preclinical data may indicate whether a particular response is likely to be a class effect.
- Exposure to physical and/or mental stresses The exposure to stress might induce adverse changes in the recipient and provide a logical and better explanation for the event.
- The pharmacology and pharmacokinetics of the study drug The known pharmacologic properties (absorption, distribution, metabolism, and excretion) of the study drug should be considered.

7.3.4. Expedited AE Reporting Period

- Any medical condition that is present at the time that the participant is screened will be considered as baseline and not reported as an AE. However, if any pre-existing medical condition increases in severity after starting study treatment, it should be recorded as an AE.
- Although disease progression including hospitalization for COVID-19 will be collected as AEs, SAEs of disease progression will be considered expected for EIDD-2801 in this protocol and will not be reported as SUSARs.

7.3.5. Pregnancy and Exposure During Breastfeeding

If a pregnancy is reported, the investigator will record pregnancy information on the appropriate form and submit it to the sponsor within 24 hours of learning of the pregnancy in a female participant or female partner of male participant (after obtaining the necessary signed informed consent from the female partner).

Although pregnancy and infant exposure during breastfeeding are not considered AEs, any pregnancy or infant exposure during breastfeeding in a participant (spontaneously reported to the investigator or their designee), including the pregnancy of a male participant's female partner, that occurs during the study are reportable to the Sponsor as described in Section 7.3.

All reported pregnancies must be followed to the completion/termination of the pregnancy.

Any pregnancy complication will be reported as an AE or SAE.

The medical reason (example: maternal health or fetal disease) for an elective termination of a pregnancy will be reported as an AE or SAE. Prenatal testing showing a fetus will be born with severe abnormalities/congenital anomalies that leads to an elective termination of a pregnancy will be reported as an SAE for the fetus.

Pregnancy outcomes of ectopic pregnancy, spontaneous abortion, missed abortion, benign hydatidiform mole, blighted ovum, fetal death, intrauterine death, miscarriage, and stillbirth must be reported as serious events (Important Medical Events). If the pregnancy continues to term, the outcome (health of infant) must also be reported.

